3.1 STUDY OUTCOME MEASURES**Primary outcome:**

- Absolute change in insulin basal rate over 24 hours after 3 rounds of basal rate testing (calculated by the sum of absolute changes for each 1 hour block compared with baseline)

Secondary outcomes:

- Healthcare professional time spent with subject
- Mean sensor glucose from continuous glucose monitoring after 3 rounds of basal rate testing
- Mean sensor glucose from continuous glucose monitoring after 1 round of basal rate testing
- Number of healthcare professional contacts
- CGM outcomes
 - %time in hypoglycaemia (<2.8mmol/L)
 - %time in hypoglycaemia (<3.3mmol/L)
 - %time in hypoglycaemia (<3.9mmol/L)
 - %time in target (3.9-10mmol/L)
 - %time spent in hyperglycaemia (>10mmol/L)
 - Measures of glycaemic variability
 - Mean glucose
 - Glucose SD
- Severe hypoglycaemia
- Insulin outcomes
 - Number of insulin time blocks changed
 - Number of insulin basal rate changes
 - Change to total daily insulin dose
- Basal insulin:bolus insulin ratio
- Healthcare professional qualitative feedback

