Participants will be asked to record their blood glucose levels using capillary blood glucose testing a minimum of four times per day – before meals, before bed, and if they feel unwell. These results will be reviewed by the researcher via telephone on day 1, 2 and 4 of pump therapy, and insulin pump settings will be adjusted if needed, based on the criteria below:.

1. Insulin to carbohydrate ratios will be changed by 10% in the event of two values being <4mmol/l within four hours of the meal, or >12mmol/l 4 hours after the meal, in the absence of a precipitating factor
2. Insulin basal rates will only be adjusted in the case of:

- Severe hypoglycaemia
- Recurrent hypoglycaemia (<4mmol/L) at the same time on 3 consecutive days
- Recurrent hyperglycaemia (>12mmol/L) at the same time on 3 consecutive days

The use of temporary basal rates during exercise and activity will be standardised. Participants will be asked to refrain from exercising and using temporary basal rates during the fasting basal rate testing.

Fasting basal rate tests

Participants will undertake a series of fasting basal rate testing commencing on day 7, 14 and 28 of insulin pump therapy. The basal rate testing protocol is as follows:

Day 1 Overnight testing with self-monitoring at 22:00, 00:00, 02:00, 04:00 and 06:00

Day 2 Omit breakfast with self-monitoring at 06:00, 08:00, 10:00: 12:00

Day 3 Omit lunch with self-monitoring at 12:00, 14:00, 16:00, 18:00

Day 4 Omit evening meal with self-monitoring at 18:00, 20:00, 22:00, 00:00, 02:00, 04:00, 06:00

Visit 4 and 5 (Day 11 and 18 of pump therapy)

Insulin pumps and CGM will be downloaded, and insulin basal rates will be adjusted based on the fasting basal rate testing as follows:

- Glucose rise more than 1.7mM during sleep or over a 4 hour period when fasting, increase basal rate by 10% for 2 hours at start of rise
- Glucose fall more than 1.7mM during sleep or over a 4 hour period when fasting, reduce basal rate by 10% for 2 hours at start of fall

Visit 6 (Around day 32 of insulin pump therapy)

Insulin pump and CGM will be downloaded. Participants will be asked to repeat the questionnaires to measure awareness of hypoglycaemia (Gold), hypoglycaemia fear (HFS), general quality of life (WHOQoLBref), diabetes distress (DDS-2) and diabetes quality of life (DQOL). Blood samples to repeat HbA1c will be taken. Pump and CGM downloads will be reviewed, and pump settings adjusted to optimise blood glucose control.

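### The primary outcome adds up basal-rate changes made by staff who can see the arm; the Visit 4 and 5 rule narrows that judgement but does not remove it, and Visit 6 has no rule

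*Combined protocol and SAP*

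**What the plan says.** Section 3.1 defines the primary outcome as the absolute change in basal rate over 24 hours after three rounds of basal testing, "calculated by the sum of absolute changes for each 1 hour block compared with baseline". Section 7 repeats this and compares the arms by a two-tailed independent t test.

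Section 6 gives three occasions on which basal rates can change:

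- **Telephone reviews.** "These results will be reviewed by the researcher via telephone on day 1, 2 and 4". The triggers are limited ("Insulin basal rates will only be adjusted in the case of", followed by severe hypoglycaemia, or recurrent low or high values at the same time on three consecutive days). No size of basal change is given.
- **Visits 4 and 5 (days 11 and 18).** "insulin basal rates will be adjusted based on the fasting basal rate testing as follows". The falling-glucose trigger is "Glucose fall more than 1.7mM during sleep or over a 4 hour period when fasting", with a mirror-image trigger for a rise. The action for a rise is "increase basal rate by 10% for 2 hours at start of rise".
- **Visit 6 (around day 32).** "Pump and CGM downloads will be reviewed, and pump settings adjusted to optimise blood glucose control". No trigger, size or duration is stated.

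Test rounds are scheduled "commencing on day 7, 14 and 28 of insulin pump therapy", so the third round ends at Visit 6.

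On masking, section 6 calls only the CGM blinded. Participants start the pump in pairs from one arm, with rates calculated beforehand and programmed at Visit 3. Pumps are downloaded at Visits 4, 5 and 6. Section 8.2 lets the clinician depart from protocol treatment at any stage, asks that reasons be recorded, and keeps the participant in the analysis.

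**The concern.** In most trials an unmasked clinician can influence the outcome only indirectly. Here the setting that staff program is itself the quantity summed, so any tendency to adjust one arm more readily becomes a treatment difference. The expectation also has a direction, because the hypothesis in section 1.2 is that circadian rates start closer to optimal. Slightly readier adjustment in the flat arm would reproduce that result with no real difference in fit, and the t test could not tell the two apart.

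The stake is not mainly the p-value. Section 7 describes a pilot meant to show the effect size, and a bias of this kind goes straight into that estimate.

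**Working it through.** **1. Can the adjusting team see the arm?** The protocol does not say so; it follows from the procedures. Initiation is in same-arm pairs, the team programs a flat or a varying profile, and it downloads the pump at each later visit. No masking of the adjuster, assessor or analyst is described.

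**2. Where does judgement remain?**

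- *Visits 4 and 5.* The period that counts as sleep is not defined. The hours 22:00 to 06:00 are tested on both Day 1 and Day 4, with no instruction if the two nights disagree. Four-hour windows overlap (for example 06:00-10:00 and 08:00-12:00 on Day 2), with no instruction on counting both. CGM is downloaded at the same visits, and the text does not say whether capillary or CGM values decide. Each of these can add or remove a step.
- *Telephone reviews.* The triggers are narrow, the size is open, and any change counts towards the difference from baseline.
- *Visit 6.* There is no rule. If the outcome is read after this visit, it includes unrestricted adjustments. If it is read before, the third round has prompted no scheduled rule-based adjustment that could enter the sum. The text does not choose.

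**3. How large is one rule step?** Section 6 sets starting basal at half of 75% of total daily dose (TDD), i.e. 0.375 × TDD. On a flat profile one step is 2 h × 10% × (0.375 × TDD / 24). As a share of daily basal this is 0.2 / 24 = 0.83%. At an assumed TDD of 50 U, daily basal is 18.75 U and one step is 0.156 U.

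**4. What could a small bias do?** The protocol gives no SD, effect size or alpha, so it has no figure to reproduce. Taken from the documents: 16 participants randomised 1:1, hence 8 per arm, and the t test. Assumed: two-sided alpha 0.05; six four-hour windows per round over two rule-governed rounds, hence 12 windows; at most one step per window; a trigger chance of 30% or 50%.

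The SD of the step count is √(12 × 0.3 × 0.7) = 1.59 or √(12 × 0.5 × 0.5) = 1.73. One extra step per participant in one arm is therefore a shift of 1/1.59 = 0.63 or 1/1.73 = 0.58 SD.

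Simulated rejection rates with no true difference, at 30% / 50% trigger chance (200,000 trials for the first row, 60,000 for the others):

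| Assumption about participants | No bias | Extra step in half of one arm | Extra step in all of one arm |
|---|---|---|---|
| Equal doses, equal trigger chance | 5% | 8.9% / 8.2% | 21.5% / 18.8% |
| TDD uniform 30-80 U | 5% | about 8% / 6-7% | about 16% / 11% |
| TDD 30-80 U and trigger chance varying between people (intraclass correlation 0.2) | 5% | about 6% / 6% | about 9% / 8% |

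The ranges are therefore about 6-9% for a step in half of one arm and about 8-22% for a step in all of it. The documents do not say how large any bias would be; the table shows sensitivity, not a forecast.

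**The case against.** The best reply is that the outcome is largely rule-driven. At Visits 4 and 5 the trigger (more than 1.7 mM), the size (10%) and the duration (2 hours) are fixed, and the tests are read at set clock times. That stands. A reader might infer that the outcome is simply a staff decision, but the documents do not support this.

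A reader might also take the undefined start of a rise or fall as the main weakness. It is not. Choosing the start mostly moves a step to other hours. On a flat profile a single step adds the same amount wherever it is placed, and on a circadian profile the amount varies only with the local rate.

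The telephone route is narrow as well. Section 4.2 admits only people with no severe hypoglycaemia in the previous year, and a three-day pattern on the pump could not be seen before the day 4 call.

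Finally, a false-positive rate of 19-22% might be read as the expected result. It is the top of the range and needs equal doses and equal trigger chances in all participants; realistic spread brings it down to about 8-9%. Letting opposing steps cancel in the hourly sum does not lower the top figure (21.9% / 19.3%).

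What the reply leaves unanswered is the set of open terms that can add or remove steps, the unsized telephone changes and, above all, Visit 6.

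**Conclusion.** The concern holds in limited form. The primary outcome is built from settings changed by a team that can see the arm, no masking of that team is described, and room for judgement remains within the Visit 4 and 5 rule, at the telephone reviews and at Visit 6. The documents do not show that bias will occur, nor that the outcome is free of rules.

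Under the assumptions listed, one extra 10%, two-hour step per participant in one arm would raise false positives from 5% to about 8-22%, and a step in half of them to about 6-9%. The position within each range depends on assumed dose range and between-person spread. That the team sees the arm is inferred from the procedures, though firmly.

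This should be corrected: a modest bias is enough to matter with 8 per arm, and the remedy is cheap.

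**What to change.** Before enrolment:

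1. The sponsor records how it reads the open terms of its own rule: the sleep period, conflicting Day 1 and Day 4 nights, overlapping windows, and capillary versus CGM values. A worksheet cannot run the rule until this is done.
2. The sponsor reconciles Visit 6 with an outcome defined after three rounds by stating whether the outcome is read before or after the Visit 6 adjustment.
3. Rule-derived changes are computed from clock time and fasting-test glucose in a locked worksheet that shows neither arm nor basal profile. Clinicians stay free to depart from its output, with reasons recorded as section 8.2 already requires.
4. Section 7 gains a sensitivity analysis of the primary outcome using only rule-derived changes, leaving out telephone changes, departures and any discretionary Visit 6 changes.

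The cost is a spreadsheet and one extra analysis, with no added staff. No clinical threshold or dose step is changed. One limit remains: glucose in later rounds reflects the settings actually programmed, so the sensitivity analysis reduces the influence of earlier discretionary changes but cannot remove it entirely.

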7. STATISTICS AND DATA ANALYSIS

This is a single site randomised study with an intervention group and a control group. The primary outcome is absolute change in insulin basal rate over 24 hours after 3 rounds of basal rate testing (calculated by the sum of absolute changes for each 1 hour block compared with baseline). This is a pilot study and will demonstrate the effect size of circadian basal rates. A post hoc power calculation will be performed.

The sample size is comparable to other diabetes technology studies, and is a realistic number for recruitment in the time period. In 2015-2016 47 people with type 1 diabetes commenced insulin pump therapy at Imperial College.

Data will be entered onto a database with restricted fields by the research team and, following data checking and cleaning, analysis will be conducted using Stata statistical software. Analysis will be conducted by [name], [name] (Reader in Human Metabolism) and the Imperial College Statistics Service. The primary and secondary outcomes will be analysed by intention to treat analysis. The difference in basal rate change between the two groups at the endpoint will be assessed by a two-tailed independent t test. Secondary outcomes will be assessed by independent t test or, if data are non-parametric, a Mann-Whitney U test. Missing data will be minimised by reducing manual data entry, using technology to collect glucose data, and by carefully supporting participants. Where present, missing data will be handled by full analysis of the available data only.

Data and all appropriate documentation will be stored for a minimum of 10 years after the completion of the study, including the follow-up period. Anonymised data will be kept on university password-protected computers in a locked room. Access is only available to the clinical research team. The identifier codes will be kept on password-protected NHS computers. The anonymised data includes CGM data, food and exercise diaries and blood test.

The paper copies of the consent forms and questionnaires will be kept in a specifically labelled FIRST1D file in a locked cupboard in the diabetes research office

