3. STUDY DESIGN

Type of study: Randomised controlled trial

Duration: 4 week trial with 1 week pre-randomisation assessment

FIRST1D protocol v1.7 23.2.18
IRAS ID: 237129

Number and type of subjects:

16 participants with type 1 diabetes referred for CSII, randomised 1:1 to circadian insulin infusion rates or flat rates.

Recruitment will be undertaken in the T1DM clinics at Imperial College Healthcare NHS Trust. Participant information sheets will be given to potential subjects who have been assessed and screened for insulin pump therapy, either in person in clinic, or via post with a participant invitation letter. After a minimum of 24 hours and following any questions, informed consent will be taken.

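### The planned post hoc power calculation has no stated difference, SD or alpha, and no confidence interval is planned for the effect size that the pilot is meant to deliver

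*Combined protocol and SAP*

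**What the plan says.** Section 3 sets the size: "16 participants with type 1 diabetes referred for CSII, randomised 1:1 to circadian insulin infusion rates or flat rates". Section 7 justifies it by precedent and feasibility: "The sample size is comparable to other diabetes technology studies, and is a realistic number for recruitment in the time period". No power, difference, SD or precision target enters that justification.

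Section 7 then gives the purpose of the study and the tool meant to support it: "This is a pilot study and will demonstrate the effect size of circadian basal rates. A post hoc power calculation will be performed".

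The primary outcome is a per-participant total, "calculated by the sum of absolute changes for each 1 hour block compared with baseline" (Section 3.1). Its analysis is a test: "The difference in basal rate change between the two groups at the endpoint will be assessed by a two-tailed independent t test". Secondary outcomes get a t test or a Mann-Whitney U test. On missing data: "Where present, missing data will be handled by full analysis of the available data only".

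No section states an alpha, a difference of interest, an SD for the primary outcome or a target power, and none plans a confidence interval for any outcome. Apart from removed names, Section 7 is complete, so redaction does not explain the gap.

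**The concern.** The stated product of this pilot is an effect size. An effect size from 16 people is useful only with a statement of how uncertain it is. The plan commits to a power figure calculated afterwards and does not commit to an interval.

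The power figure cannot do the interval's job. If it is built on the observed effect and SD, it carries no information beyond the p-value, and a non-significant result is bound to come with low power whatever the truth. If it is built on some other difference, the answer depends on a choice that the plan leaves open. In neither case does it show which differences between circadian and flat rates remain compatible with the data.

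What is at stake is interpretation. A reader could take a non-significant result with low post hoc power as a near miss, or take a point estimate as established, when the interval would show how little is settled.

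**Working it through.** **Inputs from the documents.** 16 participants, 1:1, so n = 8 per arm (Section 3); two-tailed independent t test (Section 7). No dropout rate is given and available data are analysed, so 7 and 6 per arm are shown as a range.

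**Assumptions, not in the documents.** Two-sided alpha 0.05; equal arms; roughly normal, independent data with a common SD. The figure of 16 was not derived from a power calculation, so there is no planned figure to reproduce.

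**Step 1: power from the observed effect.** The observed standardised difference is d = t × √(2/n), where t is the t value matching the p-value on 2n − 2 degrees of freedom. Power is then taken from the noncentral t distribution with noncentrality d × √(n/2). That product is t itself, so for a given n and alpha the power depends only on the p-value. With n = 8, √(2/8) = 0.5:

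| p-value | t (14 df) | d | power, 8 per arm | 7 per arm | 6 per arm |
|---|---|---|---|---|---|
| 0.05 | 2.145 | 1.072 | 51.5% | 51.7% | 52.1% |
| 0.20 | 1.345 | 0.673 | 24.1% | 23.9% | 23.7% |
| 0.50 | 0.692 | 0.346 | 9.9% | 9.8% | 9.7% |

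For 6 to 8 per arm, every result with p above 0.05 therefore shows power below about 52%.

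**Step 2: power for some other difference.** The formula is the same, with a chosen d in place of the observed one. With 8 per arm the noncentrality is 2d:

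| chosen difference | power, 8 per arm | power, 6 per arm |
|---|---|---|
| 0.5 SD | 15.4% | 12.3% |
| 1.0 SD | 46.1% | 34.7% |
| 1.5 SD | 79.7% | 65.0% |

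The same trial can be called badly underpowered or nearly adequate, depending on a number that the plan does not fix.

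**Step 3: what the interval would show.** The half-width of the 95% interval for the mean difference is t(0.975) × √(2/n), in units of the observed SD:

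- 8 per arm: 2.145 × 0.500 = 1.07 SD
- 7 per arm: 2.179 × 0.535 = 1.16 SD (1.1646 before rounding)
- 6 per arm: 2.228 × 0.577 = 1.29 SD

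With 8 per arm, p = 0.20 corresponds to 0.673 ± 1.072, or −0.40 to 1.74 SD. A p-value of 0.50 corresponds to 0.346 ± 1.072, or −0.73 to 1.42 SD. The matching power figures, 24% and 10%, convey none of this.

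**Step 4: independence.** Section 6 (Visit 3) has participants start pump therapy two at a time with someone from the same arm, so at most four pairs per arm. With within-pair correlation ρ and full pairing, the variance of an arm mean is multiplied by 1 + ρ, so the true standard error is √(1 + ρ) times the independent-data value: 1.05, 1.14 and 1.22 for ρ = 0.1, 0.3 and 0.5. In simulation with normal data and four pairs per arm, the nominal 95% t interval covered about 94%, 91% and 88% of the time. These correlations are assumed. The half-widths in Step 3 are therefore a best case.

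**The case against.** The strongest defence is that the power sentence directly follows the statement of pilot purpose, so it may loosely mean using the pilot's estimates to plan a larger trial. On that reading the difference and SD could not be named in advance, and the p-value argument would not apply. This cannot be ruled out, but the documents mention no later trial, and post hoc power normally means the power of the completed study. The interval and SD would be needed even so. At p = 0.20 with 8 per arm, the observed 0.67 SD would imply about 36 per arm for an assumed 80% power. The upper limit of the interval for the standardised effect (noncentral t, −0.35 to 1.67) would imply about 7, and that interval also includes zero.

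A second defence is that the interval comes with the planned t test and the plan does not exclude it. That is true, and it makes the missing interval a gap in what is promised, not in what can be done. But the plan promises the power figure and is silent on the interval.

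A reader might also infer more than the text supports:

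- That 16 is too few. Feasibility is an acceptable basis for a pilot, and the plan does not claim that 16 came from a power calculation.
- That the calculation will certainly use the observed effect. "A post hoc power calculation will be performed" does not say which effect is used.
- That any other difference will be picked after the results are known. The plan does not say when the inputs are fixed, so it could happen, and no more than that.

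**Conclusion.** The point holds. Section 7 commits to a power calculation with no stated inputs and to no interval for the quantity that the pilot exists to estimate. On the usual meaning, the power figure repeats the p-value: 51%, 24% and 10% at p = 0.05, 0.20 and 0.50 with 8 per arm. With another difference, it can run from 15% to 80% over 0.5 to 1.5 SD. If a later trial is meant, the text should say so.

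The informative quantity is the interval: about ±1.07 SD with 8 per arm and ±1.29 SD with 6, if participants are independent, and too narrow if outcomes correlate within the same-arm pairs. At that width the study can estimate the effect size, but it is unlikely to demonstrate one.

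The figures rest on an assumed two-sided alpha of 0.05, equal arms and roughly normal data. The argument that observed power restates the p-value does not depend on the particular alpha.

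The weight is modest. This point does not touch the primary estimate, the primary test or the sample size, and no decision rule uses the power figure. The harm is confined to what the pilot can conclude about effect size, but that is its stated purpose.

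**What to change.** In Section 7, delete the post hoc power sentence and commit instead to reporting:

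- the between-arm difference in the primary outcome, in its own units, with its 95% confidence interval from the planned t test;
- the SD of the primary outcome in each arm.

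Describe the pilot as estimating the effect size, not demonstrating it. Add a sentence noting that the interval treats participants as independent and will be too narrow if outcomes correlate within the pairs who start together.

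If any power calculation is kept, state its difference and alpha, and the source of its SD, before the data are seen, and do not use the observed effect. If the intention is to plan a later trial, say so and base that planning on the interval and the SDs.

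The cost is a few sentences in the analysis section. Conduct, eligibility, sample size and the primary test stay as they are.

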Participants will be taught to insert and replace a Dexcom G4 sensor for use with blinded CGM. They will be asked to wear it for one week prior pump initiation, and continuously after pump initiation until the end of the study. Each sensor lasts for 7 days so participants will learn to replace them themselves. They will be asked to keep a food and exercise diary during the pre-pump CGM week, and during week 4 of insulin pump therapy. Participants will be given copies of the data from the CGM at the end of the study. Diabetes self-management will continue as usual. Participants will be asked to complete questionnaires to measure awareness of hypoglycaemia (Gold), hypoglycaemia fear (HFS), general quality of life (WHOQoLBref), diabetes distress (DDS-2) and diabetes quality of life (DQOL), which will be repeated at the end of the study. Self-help leaflets from Diabetes UK will be available in case participants find these questionnaires distressing, and can approach the researcher for signposting for further help. During this session participants will be randomised to a flat basal rate or circadian rate (defined by Roche Accu-Chek software using a predefined algorithm).

Visit 3 – CSII initiation– 3-4 hours

Participants will initiate CSII in pairs from the same randomisation group, at the metabolic day ward in St Mary's hospital on a Monday. They will be taught how to use their insulin pump by a diabetes specialist dietitian trained in insulin pump therapy. They will be asked to take half their usual background insulin the night before, or to exclude the morning dose if they are on twice daily background insulin. Participants will learn to set up the pump, insert the cannula, and learn how to make adjustments to the settings. Both arms will receive half of 75% of their pre-pump total daily insulin dose via basal rates. These basal rates will be calculated in advance ready for programming at the CSII initiation visit.

Participants will receive the research dietitian's contact details for queries in working hours, and will be given a 24 hour product support number in case of pump failure. They will receive

FIRST1D protocol v1.7 23.2.18

IRAS ID: 237129

structured information on what to do manage high and low blood glucose levels. They will be instructed to return to injections in case of pump failure.

Between visits 3 and 4

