At the end of the study, participants will continue using their insulin pumps if they wish, but will return the CGM. They will be followed up in specialist type 1 insulin pump clinics, as per usual care.

Blood samples will be analysed in the Imperial College Healthcare NHS Trust laboratory and discarded after analysis.

FIRST1D protocol v1.7 23.2.18

IRAS ID: 237129

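### The CGM outcome set after three test rounds has almost no data behind it, most CGM outcomes have no time window, and the pre-pump CGM week goes unused

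*Combined protocol and SAP*

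**What the plan says.** **Outcomes.** Section 3.1 anchors two mean-glucose outcomes to events: one after the first round of basal testing, the other "Mean sensor glucose from continuous glucose monitoring after 3 rounds of basal rate testing". Neither has a start day, end day or length. The percentage-time outcomes, glucose SD and glycaemic variability have no anchor.

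**Schedule.** Section 6 states: "Participants will undertake a series of fasting basal rate testing commencing on day 7, 14 and 28 of insulin pump therapy". Each round has four test days, and the fourth runs to 06:00 the next morning. Visits 4 and 5 are on days 11 and 18, and the last visit is "Visit 6 (Around day 32 of insulin pump therapy"). At the end of the study "participants will continue using their insulin pumps if they wish, but will return the CGM".

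**Baseline.** Blinded CGM is also collected before treatment: "They will be asked to wear it for one week prior pump initiation". Food and exercise diaries are requested for that week and for week 4 of pump therapy.

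**Analysis.** Section 7 gives one sentence: "Secondary outcomes will be assessed by independent t test or, if data are non-parametric, a Mann-Whitney U test". On missing data it says: "Where present, missing data will be handled by full analysis of the available data only". The pre-pump CGM week is not mentioned.

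**Labels.** The study summary, section 3 and Appendix 1 describe the pre-pump week as preceding randomisation. Section 6 randomises at Visit 2, the session at which sensor use is first taught.

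**The concern.** An outcome defined after the last test round needs sensor data from after that round, and the schedule appears to provide almost none. The analyst would have to substitute another period: the round-3 test days, the diary week, or the stretch between rounds 2 and 3. These differ in calendar days and in whether meals are being omitted, so the choice can change the estimate itself as well as its precision. For the CGM outcomes without any timepoint the choice is wholly open.

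The second issue is efficiency. With 8 participants per arm, intervals will be wide. A week of the same measurement taken before treatment can narrow them if it correlates well enough with follow-up, and section 7 gives it no role.

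**Working it through.** **1. Timeline** (inputs from section 6). A round ends at 06:00 on its start day plus 4.

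| Round | Start | End (06:00) | Visit | Test-free stretch afterwards |
|---|---|---|---|---|
| 1 | day 7 | 7 + 4 = day 11 | 4 (day 11) | to day 14, about 3 days |
| 2 | day 14 | 14 + 4 = day 18 | 5 (day 18) | to day 28, about 10 days |
| 3 | day 28 | 28 + 4 = day 32 | 6 (around day 32) | none, beyond any slack in the visit date |

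Test results lead to basal-rate changes at Visits 4 and 5. After that, settings are next reviewed at Visit 6, when CGM stops. So all CGM collected up to Visit 6 reflects at most two rounds of test-based adjustment, even if the round-3 days are counted.

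**2. The diary week.** Appendix 1 counts pump initiation as day 0, which makes week 4 days 21 to 27. If initiation is day 1, week 4 is days 22 to 28 and touches the first overnight test. On either count, week 4 follows two rounds, not three.

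**3. Value of the baseline week.** Section 7 gives no figure to reproduce. N = 16 (8 per arm) is from section 3. Assumed, because the documents do not give them: two-sided alpha 0.05, normal outcomes, equal SD at both times, and the baseline-to-follow-up correlation ρ, shown over a range.

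Variance of the group difference, relative to the unadjusted comparison:

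- Baseline-adjusted: (1 − ρ²)(N − 3)/(N − 4) = (1 − ρ²) × 13/12.
- Change score: 2(1 − ρ).

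Half-widths are the mean 95% half-width over 60,000 simulated trials per ρ. The unadjusted half-width is 1.05 SD throughout.

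| ρ | Adjusted: variance ratio | Adjusted: half-width (SD) | Change: variance ratio | Change: half-width (SD) |
|---|---|---|---|---|
| 0 | 1.08 | 1.10 | 2.00 | 1.49 |
| 0.3 | 0.99 | 1.05 | 1.40 | 1.25 |
| 0.5 | 0.81 | 0.95 | 1.00 | 1.05 |
| 0.6 | 0.69 | 0.88 | 0.80 | 0.94 |
| 0.7 | 0.55 | 0.79 | 0.60 | 0.82 |

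Adjustment breaks even where (1 − ρ²) × 13/12 = 1, so ρ = √(1/13) = 0.277. A change score is less precise than the unadjusted comparison below ρ = 0.5, and less precise than adjustment at every value shown.

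**4. Unusable baseline weeks.** If the available-data rule drops these participants, the multiplier of (1 − ρ²) becomes:

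- one missing: (1/7 + 1/8)(12/11)/0.25 = 1.169, break-even 0.38;
- one missing per arm: (2/7)(11/10)/0.25 = 1.257, break-even 0.45.

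Filling the covariate with the overall mean of both arms keeps break-even at about 0.29 and 0.30 (simulated). At ρ = 0.5 the variance ratios are then about 0.84 and 0.85, against 0.75 × 1.169 = 0.88 and 0.75 × 1.257 = 0.94 with those participants dropped.

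**The case against.** Several points on the other side stand.

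- *The window is not wholly undefined.* Two mean-glucose outcomes have event anchors, the visit date of around day 32 allows some slack, and the matched diary weeks hint at an intended pair of periods. So it would be too strong to say that no data can exist, or that nothing is specified. But slack is not a planned window, no text ties the diary week to the analysis, and week 4 does not follow round 3.
- *The analysis form is not a three-way choice.* A reader might infer that follow-up value, change and baseline adjustment are all open under section 7. They are not. Neither named test takes a covariate. Where the protocol means change it says so, as for basal rate and total daily dose, while the CGM items are worded as levels. Baseline adjustment is a proposed improvement.
- *The gain is uncertain.* Baseline is on injections and follow-up on a pump, so a high ρ cannot be presumed. In simulation the adjusted interval was the wider one in 58% of single trials at ρ = 0.3, 43% at 0.4 and 28% at 0.5. The normal model also fits skewed percentage-time outcomes poorly.
- *The pilot's purpose.* The statement "This is a pilot study and will demonstrate the effect size of circadian basal rates" directly follows the primary-outcome definition. It does not set a precision target for the CGM outcomes.
- *The baseline week is not shown to be contaminated.* A reader might infer this from randomisation at Visit 2. The documents do not support it: on either reading the week precedes pump start, the CGM is blinded and self-management continues as usual.

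**Conclusion.** The window point holds and comes first. As scheduled, sensor data after round 3 are limited to whatever slack the Visit 6 date provides, and most CGM outcomes have no timepoint. This follows from the documents' own days and needs no assumption.

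The baseline point holds as a missed gain in precision. The unadjusted comparison is valid and unbiased. Adjustment is worthwhile only if ρ exceeds about 0.28. At ρ = 0.5 it shortens the mean half-width from 1.05 to 0.95 SD, and at 0.7 to 0.79 SD. Those sizes rest on assumed ρ, normality and 8 complete participants per arm.

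The timing conflict over randomisation is a minor labelling matter, and the week can serve as a baseline covariate either way. Only secondary outcomes are touched. The changes should be made before analysis, but the trial's validity does not depend on them.

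**What to change.** 1. **Window.** Restate the outcome over a fixed period that existing wear covers. Preferably this is seven days, matching the baseline week in length and free of meal-omission tests. Days 21 to 27, counting initiation as day 0, would do and roughly match the diary week. Label it as following two rounds of adjustment and apply it to every CGM outcome. Give the days for the outcome after one round in the same way; about three test-free days are available (day 11 to day 14).
2. **Baseline.** For continuous CGM outcomes, prespecify a linear model of the follow-up value on arm plus the same measure from the pre-pump week. Report the estimate and 95% CI on the original scale, or a scale that can be back-transformed; a rank-scale model would not give a usable effect size. Report the t test or Mann-Whitney result alongside. Do not use a change score.
3. **Missing baselines.** Keep these participants, for example by filling the covariate with the overall mean of both arms.
4. **Labels.** Reconcile the study summary, section 3 and Appendix 1 with Visit 2 in section 6.

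**Cost.** No new data or visits. Item 1 changes the definition of a listed outcome; keeping a true post-round-3 window would instead need longer CGM wear. Item 2 uses one residual degree of freedom, with a variance penalty of about 8% if ρ is 0 and a loss below about 0.28. Item 3 amends the available-data rule. Item 4 is wording only.
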